blood volume changes expected after a recent GDM pregnancy. HbA1c reflects average glycemic exposure over the preceding 2–3 months and is commonly used in people with diabetes to monitor long-term (~3 months) glycemic control (20). Even though the HbA1c is faster, easier, and less expensive to administer, it results in false negative findings 60–70% of the time when the OGTT detects diabetes (21,22). While chronic blood glucose concentrations influence HbA1c levels, many other factors can increase or decrease HbA1c as well, which could lead to questionable HbA1c results and poor alignment with the OGTT. HbA1c levels can be affected by genetic, hematologic, and illness-related factors, especially anemia (23).

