RBC turnover and provide viable alternatives to HbA1c as a marker of glycemia. In particular, these biomarkers are not based on hemoglobin and hence, do not depend on RBC turnover (26). Since fructosamine reflects the average levels of blood glucose during the former 1 to 3 weeks, fructosamine also mirrors a poorly controlled glucose metabolism better than HbA1c (27). However, some physiological and pathological conditions can significantly influence the metabolism of fructosamine. In brief, all those clinical conditions that affect protein metabolism potentially influence the concentrations of glycosylated proteins (28). Thus, physiologic or pathologic conditions linked to hypo-proteinemia (i.e., pregnancy or malnutrition) are more likely to affect the concentration of fructosamine. Another disadvantage of fructosamine is that its concentration is considerably influenced by the levels of immunoglobulins, especially IgA, which are present in abnormal concentration in a broad range of clinical conditions.(29).

Among women who experience glucose abnormalities during pregnancy, screening during the postpartum period offers a window of opportunity for early identification of diabetes and prediabetes. The rates of postpartum T2D screening with an OGTT for women with GDM are not optimal given the majority of women with GDM fail to return for postpartum glucose testing. A new device called a continuous glucose monitor or “CGM” is a small disc that is placed on the arm and can be easily placed and removed by the person wearing it. It is worn for 10 days and can stay in place for activities such as sleeping and showering. Over 10 days, over 1000 sugar measurements are taken without the person wearing the device having to do any testing (30). Continuous glucose monitoring (CGM) systems have been recognized as an ideal method of monitoring glycemic control in diabetic patients (30,31). The data of rigorous 24 h glucose profiles from CGM allow the calculation of glycemic variations, detection of asymptomatic hypoglycaemia and accurately depict the characteristics of blood glucose fluctuations (30,31). In the past decade, CGM has been proven to have similar accuracy to self-monitoring of blood glucose (SMBG) and yet provides better therapy optimization and detects trends in glucose values due to higher frequency of testing. Although CGM has been used successfully in T1D and T2D patients (31), the effectiveness of CGM in improving pregnancy outcomes

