#### STUDY OBJECTIVE

Given the damaging effect of prolonged undetected hyperglycemia, prevention and early diagnosis of T2D is cost-saving and of public health importance. This research study is being done to assess if using a glucose sensor (also known as a continuous glucose monitor or CGM) after childbirth can help identify women who are at risk of developing diabetes after having diabetes during pregnancy or gestational diabetes. Currently, screening for diabetes after childbirth is performed with an oral glucose tolerance test 4-16 weeks after delivery, but this is burdensome and most patients are non-compliant. This study will use a CGM worn on the skin for 10 days. The data from the sensor will be compared to the standard oral glucose tolerance test as well as a HbA1c and fructosamine test. This is a single site study from patients with recent GDM that attended the diabetes clinic at Woman's Hospital. The research team plans to enroll 50 participants aged 18 years or older into the study. Participation in the study is expected to last up to 10 days during the postpartum interval. Study procedures include; 1) consent and screening; and 2) sensor placement and download after 10 days of wear postpartum during which an OGTT, fructosamine and HbA1c test will be administered.

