## STUDY PLANS AND PROCEDURES

### Participants and Treatment Regimen

This is a prospective observational study of fifty postpartum women with a recent GDM pregnancy. All participants will be requested to return at 4-16 weeks postpartum for a 75 gm 2-hour OGTT as part of standard care after gestational diabetes. Fifty women with a history of GDM will be enrolled to use a blinded continuous glucose monitor (Dexcom G7). All CGM data will be masked and therefore not available to participants, clinicians, or researchers in real time. Participants otherwise will receive standard clinical care. All participants will be recruited from the Woman's Hospital Diabetes Clinic or from the maternal fetal medicine practice referring to the clinic. Those who wish to participate will provide written informed consent. The Woman's Hospital Institutional Review Board (WHIRB) will have approved both the protocol and consent.

All subjects will undergo a verbal screen, and if they are eligible and sign a medical release form, their medical records will be obtained to confirm their medical history. After consenting, demographic data, gravidity, parity, and body mass index (BMI) will be obtained. The patient's physician will be notified of participation in the study and have access to the laboratory results.

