#### Statistical analysis

Statistical analyses will be performed using SPSS version 15.1 for Windows (SPSS, Inc.; Chicago, IL). Continuous variables will be tested for normality of distribution using the Kolmogorov-Smirnov test. When necessary, non-normally distributed data will be subjected to logarithmic or square-root transformation to obtain a normal distribution where necessary for subsequent analyses. Continuous parameters will be given as means  $\pm$  standard deviations or medians with interquartile ranges (IQR). Results will be presented as mean  $\pm$  standard deviation for normally distributed continuous variables and as medians, with the 25th and 75th IQR for non-normally distributed variables. Categorical data will be presented as percentage. Pearson correlation coefficient ( $r$ ) and the significance for it ( $p$ ) will be calculated between the variables. The chi square test will be used to compare categorical variables. Chi-square test will be used to test differences in percentage proportionality Student t tests will be used to compare normally distributed groups; otherwise, Mann-Whitney rank sum tests will be used. Multiple groups will be compared using Kruskal-Wallis one-way ANOVA with a Dunn's test for pairwise comparisons when appropriate. A two-sided P-value  $< 0.05$  is considered statistically significant.

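### CGM is to be compared with the OGTT, HbA1c and fructosamine in the same women, but no planned analysis tests whether it tracks the OGTT better or worse than either blood test.

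*Combined protocol and SAP*

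**What the plan says.** The STUDY OBJECTIVE section of the combined protocol and SAP states: "The data from the sensor will be compared to the standard oral glucose tolerance test as well as a HbA1c and fructosamine test". It also gives the sample size: "The research team plans to enroll 50 participants aged 18 years or older into the study". Every woman is to have the sensor, the OGTT, HbA1c and fructosamine, so the data are paired.

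The Statistical analysis section relates one continuous measure to another only through a Pearson coefficient and its significance, which "will be calculated between the variables". It does not name the variables. For categories it says: "The chi square test will be used to compare categorical variables". The t, Mann-Whitney and Kruskal-Wallis/Dunn tests compare groups of women. Each test is judged at two-sided 0.05. The section contains no test of two dependent correlations, no paired AUC comparison and no McNemar test.

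The Background explains why the relative standing of the tests is of interest. Of HbA1c it says that "it results in false negative findings 60–70% of the time when the OGTT detects diabetes". Of glycated serum proteins such as fructosamine it says that they may "provide viable alternatives to HbA1c as a marker of glycemia".

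**The concern.** CGM asks for 10 days of wear and an extra hospital visit, while HbA1c and fructosamine each need a blood sample. A reader of the results will therefore want to know whether CGM follows the OGTT more closely than those tests do. That is a question about the difference between two correlations sharing one variable, measured in the same women. The planned output answers a different one: whether each correlation, taken alone, differs from zero.

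If CGM reached p<0.05 against the OGTT and HbA1c did not, the report could easily say that CGM did better, although the two may be equal. If both reached p<0.05, it could call them similar although one is clearly stronger. The CGM-HbA1c and CGM-fructosamine correlations do not settle the matter either. They show how far CGM agrees with those tests, not which measure lies closer to the OGTT.

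**Working it through.** **Inputs from the documents.** n = 50, all tests in the same women; two-sided 0.05 per test. The plan gives no power, effect size or precision target for 50, so there is no figure of its own to reproduce.

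**Assumptions, not in the documents.** Multivariate normal data; true r of each test with the OGTT from 0.2 to 0.6; correlation between the tests from 0.3 to 0.7.

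**Step 1: threshold for one r.** The critical t on 48 df is 2.011, so |r| must exceed 2.011/√(48 + 2.011²) = 0.279. Power for one r is approximately Φ(atanh(r)·√47 − 1.96): 28% at r = 0.2, 56% at 0.3, 83% at 0.4 and 96% at 0.5. For true r near the threshold, significance is close to a coin toss for each test.

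**Step 2: how often equal tests split.** The table shows the share of simulated studies (20,000 per setting) in which exactly one of two equally good tests has p<0.05. Ranges within a cell cover repeat runs.

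| True r with OGTT (both tests) | Tests correlate 0.3 | 0.5 | 0.7 |
|---|---|---|---|
| 0.2 | 34% | 29% | 22% |
| 0.28 | 42% | 35% | 26% |
| 0.3 | 40–41% | 34% | 26% |
| 0.4 | 24–25% | 21% | 16% |
| 0.5 | 6% | 5–6% | 4–5% |
| 0.6 | 0.5% | 0.5% | 0.4% |

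By symmetry, half of each figure favours CGM: about 17% at true r 0.3 with the tests correlating 0.5.

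**Step 3: the direct test.** For r1 and r2 with the OGTT and r12 between the tests, Williams' statistic is

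T = (r1 − r2)·√{ (n−1)(1+r12) / [ 2((n−1)/(n−3))·D + r̄²(1−r12)³ ] }, on n−3 df,

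where D = 1 − r1² − r2² − r12² + 2·r1·r2·r12 and r̄ = (r1 + r2)/2.

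Suppose the observed values are r1 = 0.40 and r2 = 0.20, with r12 = 0.5. Taken separately, p = 0.004 and p = 0.16. Then D = 1 − 0.16 − 0.04 − 0.25 + 0.08 = 0.63 and r̄ = 0.30. T = 0.20·√{73.5/[1.3136 + 0.0113]} = 1.49 on 47 df, so p = 0.14. The contrast in p-values looks decisive; the direct test does not support it. When the tests are truly equal, Williams' test declares a difference in about 5% of simulated studies.

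**Step 4: the opposite error.** With true r of 0.60 and 0.35, and the tests correlating 0.5, both are significant in about 71% of studies. Two significant results therefore say little about equality.

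**Step 5: precision of the direct comparison.** At true r 0.3 for both and r12 = 0.5, the simulated SD of the difference in r is 0.136, so the 95% half-width is about 1.96 × 0.136 = 0.27. Power to detect 0.5 against 0.3 is 26%, 34% and 52% when the tests correlate 0.3, 0.5 and 0.7.

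**Step 6: direction matters.** Time in range should fall as glycemia worsens, while HbA1c rises. With equally strong tests at −0.3 and +0.3, correlating −0.5, the unaligned Williams test declares a difference in 70% of simulated studies. Measures must be oriented the same way first.

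**The case against.** The strongest reply is that the plan only says r and p will be calculated. It states no rule for ranking tests by significance and no superiority claim, r is shown beside p so readers can see magnitudes, and women are also classified by OGTT and HbA1c category. All of this is correct. A reader might infer that the study will rank its tests by p-value, but the documents do not say so. What survives is narrower: neither the r values nor the unpaired group tests give any measure of uncertainty for a comparison between tests.

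Three further inferences go too far.

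- **A fixed error rate of about one study in three.** That figure needs true correlations of roughly 0.2 to 0.35 and a moderate correlation between tests. It falls steeply for stronger correlations, and the documents give neither input.
- **A stated aim of replacing HbA1c or fructosamine.** The STUDY OBJECTIVE section asks whether CGM can help identify women at risk, and it is the burden of the OGTT that motivates the sensor. HbA1c and fructosamine can be read as further comparators. Even so, any better, worse or similar statement would need a paired analysis.
- **A CGM measure that mirrors HbA1c must share its 60–70% miss rate.** That rate belongs to a diagnostic cut-off. The same women would be missed only at an equivalent CGM cut-off, and none is specified.

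It is also fair to object that a direct test will often be inconclusive with 50 women. That is a reason to show the interval.

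**Conclusion.** The concern holds in this limited form: the plan announces a comparison of CGM with the OGTT, HbA1c and fructosamine in the same women, but contains no paired analysis that could support a statement about which test tracks the OGTT better, worse or equally well. This follows from the text and depends on no assumed correlation.

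The size of the possible error does depend on assumptions. With 50 women and normal data, equal tests split on significance in 34% of studies at true r 0.3 with the tests correlating 0.5. The range is about 4% to 42% over true r 0.2 to 0.5 and between-test correlation 0.3 to 0.7, and under 1% at true r 0.6. These figures apply only if someone reads a split in significance as a difference, which the plan does not prescribe.

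A reader might also want BMI treated as a competing marker. The plan says only that "demographic data, gravidity, parity, and body mass index (BMI) will be obtained", as baseline description, so that comparison is not part of this point.

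**What to change.** Change the Statistical analysis section as follows.

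1. Name one primary CGM metric and one primary OGTT value (for example 2-h glucose) in advance. Label other combinations exploratory. Without this, three CGM metrics, two OGTT values and two comparators would give 3 × 2 × 2 = 12 comparisons, each at 5%.
2. Orient every measure so that higher means worse glycemia, for example by reversing time in range.
3. In women with all the tests, report the difference in correlation with the OGTT for CGM minus HbA1c and for CGM minus fructosamine. Give a 95% confidence interval from a dependent-correlation method (Williams/Steiger) or a bootstrap over women.
4. Base any better, worse or similar statement only on that interval.
5. Report the CGM-HbA1c and CGM-fructosamine correlations as descriptive.

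The cost is SAP wording and a few lines of analysis on data already being collected. The drawback is a wide interval: about ±0.27 with 50 complete sets at true r 0.3 and between-test correlation 0.5, and wider if fewer women have every test. Power is about 34% for 0.5 against 0.3 at that between-test correlation. Comparative claims will look less decisive.

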## Background

Gestational diabetes mellitus (GDM), a complication of glucose intolerance with first recognition in pregnancy, is one of the most common medical problems in pregnancy and strongly linked with the development of type 2 diabetes (T2D) later in life (1–3). Thirty percent of women with GDM will have persistent postpartum dysglycemia, and up to 70% ultimately receive the diagnosis of T2D within 10 years postpartum (4,5). Therefore, postpartum blood glucose screening is important to detect prediabetes and T2D, allowing timely treatment (3-7). For this reason, both the American Diabetes Association (ADA) and American College of Obstetrics & Gynecology (ACOG) recommend a 2-h 75-gram oral glucose tolerance test (OGTT) for all women who had GDM 6–12 weeks after delivery to detect persisting glucose intolerance or diabetes mellitus after pregnancy (8).

Unlike other laboratory tests performed, the OGTT involves several phases, including the need to fast for several hours, to drink a concentrated glucose solution which can induce unpleasant gastrointestinal effects, the collection of three to four blood samples, and the need to remain seated in the laboratory for two to three hours (9). Ingestion of the glucose solution is an important cause of discomfort for patients undergoing an OGTT. Less than half of the women who had GDM comply to the recommendations of postpartum 75-gram OGTT diabetes screening and the majority do not attend any screening for T2D postpartum (10-12). The average compliance rate for postpartum OGTT testing is 35%, largely related to women perceiving the test as inconvenient (13-15). For example, in England, a study which examined postpartum glucose screening rates in women with a history of GDM, using a nationally representative sample from 127 urban and suburban primary care practices, found that just 18.5% of women had glucose screening within six months of birth [16]. Additional studies have identified reasons for non-attendance or non-completion from the perspective of women (17-19); these reasons included: time pressures, lost laboratory forms, not knowing a test was necessary (15,19) feelings of emotional stress while adjusting to a new baby and fear of a T2D diagnosis [(17-19).

The recommended diabetes screening test postpartum is the OGTT, as hemoglobin A1c (HbA1c) is less sensitive to the rapid glycemic variations and

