#### HbA1c, Fructosamine and OGTT data

We will use the glucose levels and HbA1c values as defined by the American Diabetes Association (ADA) guidelines(8) for the diagnosis of normal, prediabetes, and type 2 diabetes. Following the guidelines of ADA, a fasting blood glucose (FBG) below 126 or 2-h blood glucose (2hBG) < 140 mg/dl is considered normal glucose tolerance; FBG of 100-125 mg/dl or 2-h blood glucose (2hBG)  $\geq$  140- 199 mg/dl is classified as prediabetes, and FBG above or equal to 126 mg/dL or 2-h blood glucose (2hBG)  $\geq$  200 mg/dl in a standard oral glucose tolerance test (OGTT) as diabetic. The reference ranges for HbA1c results are:

- No diabetes: below 5.7%
- Borderline/prediabetes: 5.7% to 6.4%
- Diabetes: 6.5% or higher (8)

Fructosamine results may be considered alongside the HbA1c and other tests.

- In non-diabetics with normal albumin, fructosamine levels normally range between 175-265umol/L (micromoles per liter). For people with uncontrolled diabetes, the fructosamine range is 268-870 millimoles per liter (mmol/L). The concentrations of fructosamine corresponding prediabetes and diabetes clinical cut-points of 5.7% and 6.5% for HbA1c, based on percentiles, were 241.4 umol/L (the 77.1 percentile) and 270.2 umol/L (the 96.5 percentile), respectively (36).

Collection of glucose data The blinded glucose monitoring data on glycemia will be retrospectively assessed. The participant data collected from the CGM (Dexcom G7) will be downloaded with the Dexcom G7 reader and uploaded to Dexcom CLARITY

The percentage of time-in-target range, time hypoglycemia, and time hyperglycemia will be reported as either means with standard deviations (SD) or medians with interquartile ranges (IQR), depending on variable distribution. For analyses assessing overnight glycemia, daytime is defined as 5:00 AM to 11:59 PM and nighttime as 12:00 midnight to 4:59 AM

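### Two-group comparisons use Student's pooled-variance t test on the strength of normality alone; Welch's version is a cheap, minor improvement for groups likely to be unequal in size

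*Combined protocol and SAP*

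**What the plan says.** The Statistical analysis section tests continuous variables for normality with the Kolmogorov-Smirnov test. Where that fails, "non-normally distributed data will be subjected to logarithmic or square-root transformation to obtain a normal distribution". The two-group rule is then: "Student t tests will be used to compare normally distributed groups; otherwise, Mann-Whitney rank sum tests will be used". For more than two groups: "Multiple groups will be compared using Kruskal-Wallis one-way ANOVA with a Dunn's test for pairwise comparisons when appropriate". The threshold is: "A two-sided P-value $< 0.05$ is considered statistically significant".

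The section does not mention unequal variances or a Welch version, does not say which two groups the t test compares, and plans no confidence interval.

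Three other places bear on group size. The Study Objective section gives the total: "The research team plans to enroll 50 participants aged 18 years or older into the study". The section on HbA1c, fructosamine and OGTT data sets cut-offs "for the diagnosis of normal, prediabetes, and type 2 diabetes", which makes three classes, not two. The Background says "Thirty percent of women with GDM will have persistent postpartum dysglycemia"; this is context from the literature, not a planning assumption. No SD for any measure appears in the document.

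**The concern.** Student's t test estimates one common variance, and the larger group dominates that estimate. If the smaller group is the more variable, the pooled standard error is too small and the test rejects too often. If the larger group is the more variable, the standard error is too large and the test rejects too rarely. A normality check detects neither, because two groups can each be normal with very different SDs.

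The study has no allocation that would balance glycemic groups. There is also some reason to expect wider spread among dysglycemic women: that group would combine prediabetes and diabetes, and the diabetic class has no upper limit. The fructosamine ranges point the same way. The plan says "In non-diabetics with normal albumin, fructosamine levels normally range between 175-265umol/L", a width of 265 − 175 = 90, while the range it gives for uncontrolled diabetes runs from 268 to 870, a width of 602. The second range is printed in different units and describes a more severe population, so it suggests a direction and not a size.

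At stake is whether a p-value from a two-group t test can be read against the stated 0.05.

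**Working it through.** The plan has no power or sample-size calculation to reproduce. The only error rate it states is the nominal 0.05, so the check is whether each test keeps to it.

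**Inputs**
- N = 50 (Study Objective) and two-sided 0.05 (Statistical analysis).
- Split: 0.30 × 50 = 15 against 35, using the Background figure. This is an inference.
- SD ratio r = SD of the smaller group / SD of the larger group. It is not in the documents; assumed range 0.5 to 3.

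**Standard error used against the true one** (larger group's SD set to 1)
- True variance of the difference: r²/15 + 1/35.
- Variance that Student's test estimates, on average: [(14r² + 34)/48] × (1/15 + 1/35).
- At r = 2 the true value is 4/15 + 1/35 = 0.2952. The pooled value is (90/48) × 0.0952 = 0.1786. The ratio of standard errors is √(0.1786/0.2952) = 0.778, so the pooled standard error is about 22% too small.
- The same formula gives 0.853 at r = 1.5 and 0.711 at r = 3.

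**Type I error by simulation** (normal data, equal means, 100,000 data sets per setting, 15 against 35)

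| SD ratio, smaller/larger group | Student | Welch |
|---|---|---|
| 0.5 | 1.3% | 4.8% |
| 0.67 | 2.3% | 4.9% |
| 1 | 5.0% | 5.1% |
| 1.25 | 7.1% | 4.9% |
| 1.5 | 9.3% | 5.1% |
| 2 | 12.9% | 5.1% |
| 2.5 | 15.1% | 5.0% |
| 3 | 16.5% | 4.9% |

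The equal-SD row calibrates the simulation: Student's test returns its nominal 5%. Repeat runs at ratio 3 gave up to 16.9% for Student's test, hence an upper figure of about 17%.

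**Sensitivity**
- Equal groups (25 against 25): Student's test stays at 4.9% to 5.5% for every ratio tried, so imbalance is necessary for the problem.
- A more uneven split (9 against 41, illustrative): 12.8% at ratio 1.5 and 28.0% at ratio 3.
- Testing variances first with Levene's test and then choosing Student or Welch (15 against 35): 6.8%, 6.6% and 5.3% at ratios 1.5, 2 and 3. This is better than Student alone but no better than using Welch directly.
- The planned Mann-Whitney alternative (15 against 35): 7.4%, 9.3% and 11.4% at ratios 1.5, 2 and 3. It is not a cure for unequal spread.

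**The case against.** The strongest reply is that the plan contains no dysglycemic-versus-normal t test. It defines three glycemic classes and sends multiple groups to Kruskal-Wallis with Dunn's test. The class definitions also overlap: a fasting value of 100 to 125 mg/dl fits the wording for both normal and prediabetes. Group sizes are therefore not fixed by the text, and those passages need reconciling. This stands. The 15/35 split illustrates an unbalanced two-group comparison; it is not a planned one.

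Second, the SD ratio is assumed, and everything depends on it. This also stands. Pregestational diabetes is excluded, which makes ratios near 3 less plausible, and there is no stated reason to expect unequal spread in variables such as BMI or parity.

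Third, whatever widens the spread of glucose measures among dysglycemic women should also raise their mean, so equal means with a two- or three-fold SD is a strained null. This limits how often the worst rows of the table would apply. It does not make the pooled standard error correct.

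Fourth, a log or square-root transformation may reduce variance differences as well as skew. It may, but it is triggered by non-normality and aimed at normality, so equal variances are not assured.

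A reader might go further and infer that 9% to 17% of the study's significant results would be false. The documents do not support that. The figures are rejection rates when the means are truly equal; the share of significant findings that are false also depends on how many real differences exist. Nor do the documents establish that the error will be inflated at all.

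**Conclusion.** A minor point that holds conditionally. The plan names the pooled-variance test with normality as its only safeguard, in a cohort whose glycemic groups will probably be unequal in size. Under the 15/35 illustration, the type I error with equal means is about 7% to 17% if the smaller group's SD is 1.25 to 3 times the larger group's, 5% if the SDs are equal, and about 1% to 2% if the ratio is 0.5 to 0.67. Both the split and the ratios are assumptions, and the documents do not show which row applies.

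The recommendation does not depend on knowing the row, because Welch's test stays close to 5% in all of them. The point applies to whatever two-group t tests are run, not to the Kruskal-Wallis comparisons.

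**What to change.** In the Statistical analysis section, replace Student's t test with Welch's unequal-variance t test for two-group comparisons of normally distributed or transformed data, with no preliminary test of variances. Report each mean difference with its Welch 95% confidence interval. The same sentence should name the groups being compared.

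The cost is one sentence, with no extra participants, visits or data. If the variances are in fact equal, some power is lost: for a 0.9 SD difference, from 81.5% to 80.3% at 15 against 35, and from 70.2% to 65.7% at a more uneven 10 against 40 (simulated; the effect size and the second split are illustrative).

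The change does not touch the Mann-Whitney route, which is also somewhat inflated under unequal spread. Results from that route should be read with this in mind.

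### With 50 women and about 30% dysglycemia, Dunn's test cannot reach p<0.05 for diabetes versus prediabetes, even if CGM orders every woman correctly

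*Combined protocol and SAP*

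**What the plan says.** The Study Objective section sets the sensor data against the OGTT, HbA1c and fructosamine. The section on HbA1c, fructosamine and OGTT data adopts ADA cut-points "for the diagnosis of normal, prediabetes, and type 2 diabetes", which gives three OGTT classes.

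The Statistical analysis section then offers two relevant methods. For more than two groups: "Multiple groups will be compared using Kruskal-Wallis one-way ANOVA with a Dunn's test for pairwise comparisons when appropriate". For groups in general: "Student t tests will be used to compare normally distributed groups; otherwise, Mann-Whitney rank sum tests will be used". The threshold is the same throughout: "A two-sided P-value $< 0.05$ is considered statistically significant". No multiplicity rule is attached to Dunn's test.

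On numbers, the section on participants states: "Fifty women with a history of GDM will be enrolled to use a blinded continuous glucose monitor (Dexcom G7". There is no power calculation and no expected count per class. The Background supplies the only prevalence figure: "Thirty percent of women with GDM will have persistent postpartum dysglycemia".

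No sentence says outright that CGM metrics will be compared across the three OGTT classes. It is the natural use of the multi-group sentence, but it is an inference.

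**The concern.** Dunn's test does not re-rank the two classes being compared. It takes their mean ranks among all women and divides the gap by a standard error built from the rank variance of the whole sample. If most women are normal and rank lowest, the prediabetes and diabetes classes are squeezed into the few top ranks. Their gap is then capped, while the standard error still reflects all 50 ranks. The better CGM separates normal from prediabetes, the less room Dunn's test has to separate prediabetes from diabetes.

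The Background gives detection of both prediabetes and T2D as the reason for postpartum screening. A CGM metric that sorted all three classes perfectly would still give a non-significant result for the two upper classes. A reader could take that as evidence that CGM does not tell them apart, when the test could not have shown it.

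**Working it through.** **Inputs.** N = 50 (participants section). 30% dysglycemic, so 0.30 × 50 = 15 (Background; not a planning assumption). Two-sided 0.05, unadjusted (Statistical analysis). The split of the 15 into prediabetes (a) and diabetes (b) is not given, so every split was tried. The figure of 50 has no stated derivation, so there is no plan calculation to reproduce.

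**Largest possible gap.** With perfect ordering, normal women hold ranks 1 to 35, prediabetes the next a ranks and diabetes the last b. The mean ranks are 35 + (a+1)/2 and 35 + a + (b+1)/2. Their difference is (a+b)/2 = 7.5 at every split.

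**Standard error.** √{[N(N+1)/12] × (1/a + 1/b)}, with 50 × 51/12 = 212.5. It is smallest at 8 and 7: √(212.5 × 0.2679) = 7.54. So z = 7.5/7.54 = 0.994 and p = 0.320. Bonferroni for three pairs would make it 0.96.

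**By split**, against the exact Mann-Whitney p at complete separation, 2/C(15, b):

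| Diabetes / prediabetes | Dunn p | Exact Mann-Whitney p |
|---|---|---|
| 1 / 14 | 0.62 | 0.13 |
| 2 / 13 | 0.50 | 0.019 |
| 3 / 12 | 0.43 | 0.0044 |
| 5 / 10 | 0.35 | 0.0007 |
| 7 / 8 | 0.32 | 0.0003 |

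**Ties.** If all 35 normal women tie (for example at 0% time in hyperglycemia), the variance term falls to 212.5 − (35³ − 35)/(12 × 49) = 139.6. The standard error at 8 and 7 is then 6.12, z = 1.226 and p = 0.22.

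**Other counts.** Best Dunn p over all splits, no ties: 0.19 with 18 dysglycemic women, 0.125 with 20, 0.077 with 22, 0.059 with 23 and 0.044 with 24 (12 and 12). With all normals tied, 23 is enough (0.040). At 30% prevalence the chance of 24 or more is 0.6%, and of 23 or more 1.2%.

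**The other comparisons, same ideal data.** At 35/8/7, Kruskal-Wallis p = 1.2 × 10⁻⁷, Dunn normal versus prediabetes p = 0.0002 and normal versus diabetes p < 0.0001. Across all splits, unadjusted, normal versus diabetes is always significant (p = 0.030 with one diabetic woman). Normal versus prediabetes is significant unless only two women (0.081) or one (0.22) have prediabetes.

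**Imperfect ordering.** Simulated power for diabetes versus prediabetes, normal data, shifts in SD from normal, unadjusted; Mann-Whitney run only after a significant Kruskal-Wallis. A repeat run agreed within about two percentage points. Shifts and splits are assumptions.

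| Normal/prediabetes/diabetes | Shifts | Dunn | Exact Mann-Whitney |
|---|---|---|---|
| 35/12/3 | +1.5, +3.5 | 0.6% | 77% |
| 35/10/5 | +1.5, +3.5 | 6% | 88% |
| 35/10/5 | +1, +2 | 12% | 33% |
| 35/12/3 | +0.5, +2 | 27% | 50% |
| 35/10/5 | +0.5, +2 | 48% | 64% |
| 35/12/3 | +0.5, +1.5 | 13% | 24% |
| 35/10/5 | +0.5, +1.5 | 26% | 33% |
| 35/10/5 | +0.25, +1.5 | 42% | 47% |

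**Error control of the alternative.** With three groups, if any two pairwise equalities hold, so does the third. The only intersection hypothesis is therefore the overall null. Testing it first at 0.05, then each pair at 0.05, is a closed procedure. Simulated family-wise error was 3.9% to 5.3%.

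**The case against.** Several points on the other side are fair.

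- **The analysis is inferred.** The plan speaks of multiple groups and applies Dunn's test when appropriate. It attaches no hypothesis or success criterion to diabetes versus prediabetes, and it lists t and Mann-Whitney tests for comparing groups. So the documents do not strictly make Dunn's the only pairwise method. This stands, and the point is conditional on the three-class reading. It does not rescue the plan: Dunn's is the only pairwise method attached to multiple groups, and the choice between p = 0.32 and p = 0.0003 should not be left until the data are seen.
- **One pair is not the whole result.** A reader might infer that an ideal CGM result would be reported as no difference. The arithmetic does not support that: the overall test would be overwhelming and the comparisons with normal usually clear.
- **0.32 is not a general floor.** A reader might take it as one. It assumes exactly 15 dysglycemic women and no ties. The 30% is background, and at that rate the chance of 16 or more is 43%. What survives is the non-significance, up to 22 or 23 dysglycemic women.
- **Perfect ordering is Dunn's worst case.** When prediabetes overlaps normal, the two tests come much closer (42% against 47% in one scenario), and both can be underpowered. This stands. Mann-Whitney still did better in every scenario tried.
- **Group p-values do not measure screening accuracy,** and Dunn's test after Kruskal-Wallis is standard practice. Both are true, and both limit the priority. Neither makes the test able to answer this contrast.

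**Conclusion.** The concern holds for one comparison. If CGM metrics are compared across the three OGTT classes, Kruskal-Wallis followed by Dunn's test cannot reach p<0.05 for diabetes versus prediabetes at 50 women and 30% dysglycemia, however well CGM performs and however the 15 women divide. This is arithmetic and needs no effect-size assumption. It would stop being true only at about 23 to 24 or more dysglycemic women, roughly a 1% event at the Background's rate.

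The size of the practical loss does rest on assumptions. It is very large when the three classes are well separated and modest when prediabetes resembles normal. With very few diabetic women, power stays limited under either test.

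Priority is minor to moderate: one clinically relevant contrast is unanswerable as written, in an observational study whose other comparisons are unaffected.

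**What to change.** In the Statistical analysis section, name the comparison of CGM metrics across the three OGTT classes and replace Dunn's test for it with a rule such as:

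*CGM metrics will be compared across the normal, prediabetes and diabetes OGTT classes by the Kruskal-Wallis test. If p<0.05, each pair of classes will be compared by an exact Mann-Whitney test on those two classes only, at two-sided 0.05. If only one woman has diabetes, her values will be described and not tested.*

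The exact test should use a permutation distribution that allows for ties, since time-in-range metrics may tie.

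The cost is one or two sentences; Mann-Whitney is already in the plan, and no extra data are needed. There are two small downsides. The error control applies only with exactly three groups, so the rule should not be carried over to comparisons of four or more. And a class of one woman cannot reach 0.05: against 14 women the best exact p is 2/15 = 0.13, and against 35 it is 2/36 = 0.056, where unadjusted Dunn could give 0.030. Hence the descriptive rule.
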